3 LIST OF ABBREVIATIONS

AE	Adverse Event	NIHR	National Institute of Health
AR	Adverse Reaction		Research
ВР	Blood pressure	NRES	National Research Ethics Service
CI	Chief Investigator	CRN	Clinical Research Network
ConSORT	Consolidated Standards of Reporting Trials	PenCTU	Peninsula Clinical Trials Unit
CRF	Case Report Form	PMG	Project Management Group
CRN	Clinical Research Network	PPI	Participant and Public Involvement
CTA	Clinical Trial Authorisation	QALY	Quality Adjusted Life Year
CTIMP	Clinical Trial of an Investigational Medicinal Product	R&D	Research and development
CTU	Clinical Trials Unit	RCT	Randomised controlled trial
DMC	Data Monitoring Committee	REC	Research Ethics Committee
GCP	Good Clinical Practice	SAE	Serious Adverse Event
GP	General Practitioner	SAR	Serious Adverse Reaction
HR	Heart rate	SkiM	Skills for weight loss Maintenance
ICER	Incremental cost-effectiveness ratio	SUSAR	Suspected Unexpected Serious Adverse Reaction
ICH GCP	International Conference on Harmonisation of Good Clinical Practice	TSC	Trial Steering Committee

4 STUDY SUMMARY

Study Title	Skills for weight loss Maintenance (SkiM): Developing an intervention to support maintenance of weight loss and a trial to evaluate it.		
Study Setting	Two community-based health service providers in Devon, UK. - Westbank Healthy Living Centre, Exminster. - Torbay and Southern Devon Health and Care NHS Trust		
Study Design	Action research feasibility design including before-and-after evaluation of two iterations of a weight management intervention, delivered in two different formats.		
Study Aims and Objectives	Aims 1. To develop a weight management intervention that specifically addresses weight loss maintenance 2. To inform development of a trial that will be used to evaluate the intervention Objectives 1. To assess the feasibility and assentability of incorporating the SkiM.		
	 To assess the feasibility and acceptability of incorporating the SkiM intervention into existing community-based weight loss programmes. To refine the SkiM intervention, so as to optimise its potential effectiveness and feasibility for incorporation into existing community-based weight management programmes. 		
	3. To assess the feasibility and acceptability to study participants of recruitment, assessment and process evaluation strategies that may be used in a future trial of the SkiM intervention.		
	4. To determine rates of participant recruitment, retention and outcomes completion at 12 months, and identify influences on these variables.		
	5. To estimate the resources needed for the planned future trial.		
	6. To develop and select process and outcomes measures for use in a future trial.		
	7. To develop the framework for economic evaluation in a future trial, including estimation of intervention costs.		
Study Participants	 People who have agreed to take part in an existing Tier 2 community-based weight loss programme delivered by one of the identified Service Provider organisations. People recruited specifically for this study by other routes. Programme provider staff (who will deliver the intervention). 		
Inclusion Criteria (participants)	 Meets eligibility criteria for existing weight management programme, with which SkiM will be combined. Adults (aged ≥18 years) Body mass index (BMI) ≥30 kg/m² (white European) or ≥27.5kg/m² (South Asian and black African/Caribbean heritage populations) Provision of informed consent to participate 		
Exclusion Criteria	Excluded by eligibility criteria of existing programmes, with which Skim		

(participants)

- intervention will be combined
- Currently pregnant, planning to be pregnant in next year, or childbirth in last 6 months
- BMI≥50kg/m²
- Clinically diagnosed eating disorder
- Medical condition (e.g. terminal illness, uncontrolled thyroid disease, dementia, psychosis) judged by medical practitioner to seriously limit capacity to manage weight.
- Concurrent participation in other weight management programmes (e.g. commercial weight loss programmes)
- Unable to understand the study information, read the study manual or complete outcome questionnaires.
- Unable to make own arrangements to travel to intervention venue
- Participating in concurrent interventional research which may overburden the participant or confound data collection.

Entry criteria (Intervention staff)

- Existing providers of selected Tier 2 weight management services in Devon to which NHS clinicians may make referrals
- Completion of the SkiM intervention training course
- Provision of informed consent to provide study data.

Target sample size

- 110 programme participants (up to 55 at each site)
- Up to 6 intervention staff to deliver the intervention (2-3 delivering the programme at each site)

Intervention

A programme in which the SkiM intervention is integrated with the existing weight loss intervention, and delivered over six months in a group format. Data gathered during the first presentation in each format will be used to refine the intervention, which will then be evaluated in a second iteration.

Study duration

Total duration: 26 months (1st March 2015 to 31st May 2018)

Mar-Jul 2015	Intervention development	
Aug-Oct 2015	Training of intervention providers	
	Recruitment for first iteration	
Oct 2015-Apr 2016	First iteration	
May-Aug 2016	Data analysis & refining intervention	
Jul-Sep 2016	Recruitment for second iteration	
Sep 2016-Mar 2017	Second iteration of intervention	
	12-month follow-up assessment of Phase 1	
Aug -Sep 2017	12-month follow up assessment of Phase 2	
Feb-Mar 2018	18-month follow up assessment of Phase 2	
Feb-May 2018	Data analysis, reporting and trial planning	

BACKGROUND AND RATIONALE

This study forms part of a programme of work on the identification and evaluation of interventions to support the *maintenance* of weight loss through lifestyle change (changes in diet and physical activity). In particular the study aims to pilot the intervention and trial procedures for a future full-scale trial to assess the cost-effectiveness of alternative strategies for supporting weight loss maintenance that have different resource requirements. The information produced by the larger, full-scale trial will help inform the commissioning of weight loss services for implementing new NICE guidance on diabetes prevention¹ and for managing obesity in the NHS.

- 1: *Impact of obesity:* Obesity is associated with a reduction in life expectancy of up to 14 years, ² primarily due to an increase in cardiovascular disease (CVD) risk. Because excess fat causes impaired glucose regulation (IGR), obesity also substantially increases the risk of developing type 2 diabetes.³ People with a BMI of 35-40kg/m² have a relative risk of type 2 diabetes 8 to 11 times higher than people of normal weight.³ Obesity is also associated with an increased likelihood of developing kidney disease, fatty liver disease, osteoarthritis, several cancers, hypertension, dementia, depression and sleep apnoea.⁴ Based on current trend in obesity prevalence (currently 23% in adults), the combined cost to the NHS and to UK society will reach £49.9 billion/year by 2050.⁵
- 2. Benefits of weight reduction: Evidence from systematic reviews shows that, in people with increased cardiovascular risk, relatively modest reductions in weight (2-5kg) reduce key cardiovascular risk factors (e.g. lipid profiles, blood pressure) to a clinically meaningful extent.^{6, 7} Weight loss also reduces insulin resistance and can prevent progression to type 2 diabetes.^{8, 9} In the Finnish Diabetes Prevention Study, a mean 3.4kg of weight loss in people with IGR, reduced the incidence of type 2 diabetes at 4 years of follow-up by 58%.⁹
- 3. Why focus on maintenance? Although lifestyle interventions are increasingly successful in promoting *initial* weight loss (after 3-6 months)^{7, 10, 11} gradual weight regain is common, with weight typically returning to baseline levels over 5-6 years.¹¹ The cost-effectiveness of using lifestyle interventions to prevent type 2 diabetes is strongly dependent on assumptions about the maintenance of weight loss: Two central assumptions of the current NICE economic model for diabetes prevention are that the prevention effect (a relative risk reduction of 16% per kg of weight loss¹²) lasts only as long as weight loss is sustained and that weight loss regresses to zero over 5-6 years.⁴ The economic case for the national (England) NHS Health Checks programme is also strongly driven by the assumed cost-savings from prevention of diabetes and cardiovascular disease following "intensive lifestyle intervention" to support changes in diet and /or physical activity. These benefits account for around 40% of the estimated savings attributed to NHS Health Checks.¹³ Hence, if the major health economic benefits of intervention to reduce diabetes risk and cardiovascular risk through weight loss are to be realised, then sustaining weight loss is a crucial issue.
- *4) What new research is needed?* More research is needed to establish effective strategies for maintenance of weight loss following initial intervention. Recent reviews of weight loss maintenance (at 1 to 4 years of follow up)^{14, 15} found that most trials had substantial methodological limitations. However, the data suggests that weight loss maintenance may be associated with the use of a) peer or social support b) frequent continued professional support c) specific 'self-regulatory' methods like goal setting, problem solving, relapse prevention, self-monitoring, and daily self-weighing.^{16, 17} Further

systematic reviews show that targeting both diet and physical activity also generates more weight loss at one year compared with either diet or physical activity alone. 4, 18, 19 Intervention effectiveness also increases with the intensity or amount of intervention delivered (total contact time or number of contacts). 19-21 However, the reviews conclude that more experimental research on the relationship between intervention intensity and effectiveness is needed. 19, 21

Intervention cost is a major constraint for NHS delivery /commissioning of obesity management services in the current economic climate. The intensive lifestyle interventions that are used in research settings are often not practical for commissioning on a large scale.^{22, 23} Hence, there is clear need to develop strategies that are realistic and affordable for future commissioners of NHS services. There have been repeated calls for experimental research to identify cost-effective methods for supporting the long-term maintenance of diet, physical activity and weight loss in government reports,² evidence-based guidelines^{4, 24, 25} and numerous systematic reviews.^{7, 11, 14, 19} The need for more research on health behaviour maintenance was also identified as one of the main recommendations of the recent House of Lords Select Committee on behaviour change.²⁶

Interim summary: People who lose weight often put it back on within a few years. The existing literature suggests some potentially useful intervention strategies. However, there is a pressing need for research to increase our understanding of longer-term maintenance of the lifestyle changes (i.e. changes in diet and physical activity) needed to achieve weight loss, and in particular to identify intervention strategies that are practical and cost-effective for use in UK healthcare settings.

Prior work to develop the SkiM intervention: Our intervention approach is informed by extensive needs assessment activities, including consultation with service users, service providers and commissioners of weight management services,²⁷ reviews of quantitative (trial) evidence,^{14, 15, 28} a review of theoretical ideas²⁹ and a synthesis of qualitative research studies on weight loss maintenance³⁰. Using MRC guidelines for developing complex interventions³¹ and rigorous intervention development techniques (intervention mapping and process mapping)^{32 33, 34} we have developed intervention materials and training materials to support weight loss maintenance. Rather than offering and evaluating these as a standalone intervention, we have incorporated them into several existing weight management programmes. This will ensure that principles and skills for behavioural sustainability are attended to from an early stage in weight management efforts.

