7 STUDY DESIGN

7.1 Summary of the study design

An action research approach ³⁵ will be used, in which the SkiM intervention is tested and developed in an iterative cycle, involving stakeholders (particularly the service users themselves) in all stages of the process. The cycle involves three iterations of the intervention: an initial version has been developed with the involvement of service users, providers and commissioners as well as academics in the field of health behaviour change; this will be subject to mixed methods evaluation including pre-post testing, the results of which will be used to develop a second iteration of the intervention, which will also be evaluated. A third version of the intervention will then be developed for formal testing in a randomised control trial. This iterative approach involving multiple stakeholders and a pre-post test design, will enable investigation of the feasibility of integrating the SkiM intervention into existing programmes, as well as issues of acceptability, demand and implementation ³⁶. It also facilitates the evaluation and further development of recruitment, assessment and retention methods to be used within a subsequent trial. It is expected that in a trial, the control group would receive best-practice

[figure not shown]
REC Ref: 15/SW/0126

SkiM study protocol v8 - 29.03.16

usual care, which would be an existing weight loss programme. Hence all participants would receive an active intervention, and the need for a control arm is less pressing in a feasibility study.

The intervention period is six months, with outcomes assessment at baseline, and at 6, 12 and 18 months post-baseline. Eighty participants will be allocated equally to one of two study arms with different programme formats: both will be group-based, but they will differ in the number of sessions and supplementary support available. The study will be staged into two cohorts of approximately 40 participants. These will be run sequentially and separated by a period of four months, during which process data collected from the first stage will be used to refine the intervention for delivery in the second phase. This design is illustrated in Figure 1.

Figure 1: Study design

STUDY PARTICIPANTS

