10.6 Expected recruitment rate

The study requires that 40 participants are recruited over a two-month period for each cohort (This figure maybe revised depending on experiences of programme and study attrition with the first cohort.) Preliminary feasibility work has established that recruitment for the study will require both the standard referral route and additional recruitment from local research-ready General Practice lists. Recruitment will be phased, with invitations sent initially to 80 people across several Practices, with subsequent mailings dependent on response and uptake rates. Assuming a 25% uptake rate, the standard referral routes are expected to produce 20 people per cohort and the Practice route will deliver 20 people per cohort. Experience in recruitment of the first cohort will determine the number of practices and patients to be approached in the second cohort.

SkiM study protocol v8 - 29.03.16

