11.3 Organisation of the intervention

After the baseline assessment the study team will pass contact details of participants on to the appropriate provider, who will contact the individual to let them know practical arrangements.

Recruitment will be organised so that the intervention can be run twice in succession, with a four-month break between. The first cohort will have 40 participants divided into four groups; depending on experience with this cohort, the second cohort may have up to 60 participants, divided into four groups, two being delivered by each provider. This process will provide the maximum experience of

SkiM study protocol v8 – 29.03.16

delivering the intervention in different contexts and groups, and the 4-month break will allow process evaluation data to be analysed and the intervention refined before it is run a second time. Figure 2 illustrates how this will occur.

[figure not shown]

Figure 2: Organisation of intervention arms

Intervention providers will inform the research team when programmes commence, so that process evaluation and follow up data collection can be scheduled appropriately.

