16.2 Sample size considerations

The sample size is calculated to provide realistic estimates (and confidence intervals (CIs)) for the recruitment and study completion rates. The resulting sample size will also allow realistic estimates of the intervention concordance rate and provide an ample pool of participants for qualitative sampling. From recent UK-based trials of interventions to support dietary /physical activity change, it is estimated that 25-30% of those contacted will take part and 70-80% of these will complete measures at 24 months^{46, 47}With a 30% recruitment rate, in order to estimate the recruitment rate with 95% CIs of +/-8% at each site, we would need to approach 133 people at each site (and this would recruit around 40 people per site). If recruitment rates vary between 20 and 50%, the CIs on the estimated recruitment rate would still be acceptable (between +/-6.8 and +/-8.5%). The total sample size requirement for two sites is therefore 80.

This sample size will also allow realistic estimates of the intervention concordance and study completion rates (+/-9 or 10%, assuming 70-80% completion) and provide an ample pool of participants for qualitative sampling (to get feedback on the intervention) in both phases of

intervention development (we would have 2 groups of 10 people receiving the intervention in each phase at each site).

Each of our provider partners will supply 2-3 intervention facilitators (5-6 in total) to deliver the study interventions. It is considered that experience of providing 2-4 complete programmes for 10-20 participants each would give the facilitators sufficient exposure to the intervention to be able to comment on its feasibility and acceptability

If intervention concordance /attendance is lower than expected, we will recruit a higher number (up to 50% more) in the second round to ensure that: a) sufficient people get exposure to the intervention to allow us to get collect a meaningful amount of data on process issues such as acceptability and possible improvements to the programme; b) the facilitators get experience of running several groups; and c) the group size does not become too low to function effectively (if this does still occur, we will consider merging groups to keep the group size above 5 if possible).

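### The summary's target of 110 participants exceeds both the requirement of 80 and the maximum of 100 that the protocol's own enlargement rule allows; the recruitment-rate precision also assumes a fixed 133 approached per site

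*Protocol*

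**What the plan says.** On the number of participants:

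- Section 4, Target sample size: "110 programme participants (up to 55 at each site", with no derivation.
- Section 7.1: "Eighty participants will be allocated equally to one of two study arms", and "The study will be staged into two cohorts of approximately 40 participants".
- Section 16.2: "The total sample size requirement for two sites is therefore 80". If concordance or attendance is lower than expected, "we will recruit a higher number (up to 50% more) in the second round".
- Section 11.3: the first cohort has 40 people in four groups, and "the second cohort may have up to 60 participants", also in four groups.

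On the precision of the recruitment rate, section 16.2 assumes 30% uptake and a 95% confidence interval of ±8% at each site. It derives 133 people to approach per site, of whom about 40 would enrol. It then adds: "If recruitment rates vary between 20 and 50%, the CIs on the estimated recruitment rate would still be acceptable", giving ±6.8% to ±8.5%. Section 10.6 requires 40 enrolled per cohort, starts with 80 practice invitations, and continues "with subsequent mailings dependent on response and uptake rates". Section 8.2 likewise allows further tranches of letters depending on recruitment.

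**The concern.** A reader who takes the target from the summary will plan for 110, and one who takes it from the design or sample size sections will plan for 80, with a conditional rise. The enlargement rule is stated twice, consistently, and does not lead to 110. The protocol therefore does not settle how many people it plans to enrol.

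The precision statement raises a separate question. It varies the uptake while keeping the number approached constant, but the recruitment plan keeps the number enrolled constant and lets the number approached vary. Recruitment rate is a named feasibility measure (section 14.1) and one of the criteria for not continuing to a trial (section 16.2.1), so its stated precision should match the way recruitment is run.

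**Working it through.** **Totals.** Inputs: first cohort 40 (11.3); second cohort up to 60 (11.3) or up to 50% more (16.2).

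- Planned: 40 + 40 = 80, as stated.
- Maximum by percentage: 40 + 1.5 × 40 = 100. Maximum by cap: 40 + 60 = 100. The two statements agree. Per site, 100 / 2 = 50.
- For 110: second cohort 110 − 40 = 70, and 70 / 40 = 1.75, an increase of 75%. Both limits are broken.
- An attrition allowance does not explain it: 80 / (1 − d) = 110 needs d of about 27%, and the protocol applies no such inflation.

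**Precision as stated.** Half-width = 1.96 × √(p(1 − p)/n), with n = 133 approached per site.

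- p = 0.30: 1.96 × √(0.21/133) = 7.8% (stated as 8%)
- p = 0.20: 1.96 × √(0.16/133) = 6.8% (as stated)
- p = 0.50: 1.96 × √(0.25/133) = 8.5% (as stated)

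The stated range therefore reproduces with n held at 133. Exactly ±8% at 30% would need 127, so 133 appears to come from 40 / 0.30 = 133.3. With 133 fixed, enrolment per site would be 133 × 0.20 = 26.6 at the low end and 133 × 0.50 = 66.5 at the high end, or about 53 to 133 over two sites. Neither end matches 40 per site and 80 in total.

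**Precision with 40 enrolled per site.** The number approached is n = 40/p, with the same half-width formula.

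| Uptake | Approached per site | Half-width, 40 enrolled | Half-width, 133 approached |
|---|---|---|---|
| 20% | 200 | ±5.5% | ±6.8% |
| 25% | 160 | ±6.7% | ±7.4% |
| 30% | 133 | ±7.8% | ±7.8% |
| 50% | 80 | ±11.0% | ±8.5% |

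The Wilson interval gives ±10.7% at 50%, so the result does not depend on the choice of formula. With n = 40/p the half-width is 1.96 × p × √((1 − p)/40). Setting this to 8.5% gives p√(1 − p) = 0.274, which is met at p of roughly 34%. Only above that uptake is the precision worse than the upper end of the range the protocol calls acceptable.

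**Completion rate.** With n = 80, 1.96 × √(0.21/80) = 10.0% at 70% and 1.96 × √(0.16/80) = 8.8% at 80%. The stated ±9 or 10% is therefore right, and it rests on 80.

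**The case against.** On the total, the best defence is that the summary gives a ceiling (up to 55 per site), that section 7.1 describes cohorts of only about 40, and that section 10.6 lets the cohort figure be revised. First cohorts of 44 (44 + 66) or 50 (50 + 60) would give 110. Spread over eight groups, 110 is 13.75 per group, within the 10-15 mentioned in section 9.2, so group size alone does not rule it out. This makes 110 workable but does not reconcile it. The protocol states neither 44 nor 50 for the first cohort, and 66 would exceed the cap of 60. The revision in section 10.6 depends on experience with the first cohort, so it can only change the second, which section 11.3 limits.

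On precision, the defence is that section 16.2 contains no arithmetic error: it is an ordinary sensitivity check on a fixed denominator. That stands. The problem is only that the fixed denominator does not fit the recruitment plan. It is also fair that ±11% is an extreme case. At 50% uptake, the initial 80 practice letters alone would fill a cohort of 40, whereas section 10.6 expects to need both recruitment routes. In practice more than 80 per site might be approached, and the interval would then be narrower.

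Some stronger readings are tempting but not supported:

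- A reader might infer three conflicting totals. The figure of 100 is not printed; it is the sum of 40 and 60, and it is compatible with 80 as the base. The conflict is 110 against both.
- A reader might infer that the wrong total undermines every precision statement. None of them uses 110, and enrolling 110 would improve completion precision (about ±8.6% at 70% and ±7.5% at 80%).
- A reader might see 25% uptake in section 10.6 and 30% in section 16.2 as a contradiction. Section 16.2 itself gives 25-30%, so each section uses one end of a stated range.

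**Conclusion.** The target of 110 in the summary conflicts with the body of the protocol. It is 30 above the stated requirement and 10 above the derived maximum, or 5 per site. This assumes a first cohort of 40, as section 11.3 states, and an equal split between sites.

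The precision point is real but secondary, and a reader should not infer that the protocol is over-optimistic throughout. With 40 enrolled per site, precision is better than stated at 20% uptake, and at the expected 25-30% it is slightly inside the stated ±8%. It is worse than the stated limit of 8.5% only above roughly 34%, reaching about ±11% at 50%. These figures assume 40 enrolled per site over both cohorts, mailings that stop when that number is reached, and the usual normal approximation. The study makes no formal between-arm comparison, and neither point threatens its validity. Both should be corrected, because the sample size and its precision are the quantities that section 16.2 sets out to justify.

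**What to change.** In section 4, replace the target with 80 planned (40 per site), rising to at most 100 (50 per site) if the enlargement rule in sections 11.3 and 16.2 is used. If 110 is intended, change the rule in those two sections instead and give the reason.

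In section 16.2, say that enrolment is fixed and the number approached follows from uptake. Restate the recruitment-rate precision for 40 enrolled per site as about ±5.5% at 20% uptake, ±6.7% at 25%, ±7.8% at 30% and ±11% at 50%. Add that the last value is an extreme case and that 8.5% is exceeded only above roughly 34%. The completion-rate precision and the 25-30% uptake assumption can stay as they are.

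The cost is wording only. One precision figure becomes less favourable at high uptake, and the figures at low and expected uptake become slightly better or stay about the same.
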